## **8. STUDY DESIGN**

### **8.1 STUDY DESIGN**

This is a multi-center, post-marketing, prospective study. Subjects will be stratified by fracture type (minimum of 45 displaced and 45 non-displaced fractures) for a minimum total of 90 enrolled subjects.

Data from eligible subjects who have provided a signed ICF will be evaluated at the pre-operative, operative/discharge, 6-weeks, 3-month, 6-month and 12-month follow-up visits.

The total study duration will include approximately 18 months for enrollment and one year of follow-up at approximately 10 sites in the United States.

### **8.2 ALLOCATION AND BLINDING**

This study is not randomized.

### **8.3 STUDY ENDPOINTS**

#### **8.3.1 Primary Endpoint**

The primary endpoint of this study is the re-operation rate for any reason of displaced and non-displaced femoral neck fractures treated with CONQUEST FN™ at one year post-operation.

### 8.3.2 Secondary Endpoints

The secondary endpoints of this study include generation of safety, performance, and health economic evidence supporting the use of the CONQUEST FN™ Femoral Neck Fracture System per the endpoints listed below:

- Intraoperative complications
- Radiographic outcomes including quality of fracture reduction
- Construct failure past typical femoral neck fracture healing period (past 6 months)
- Visual analogue scale (VAS) relating to pain at the fracture site
- Quality of Life (EQ-5D-5L)
- Time to return to full weight-bearing
- Ambulatory status from pre-injury to study completion
- Timed Up & Go
- Length of hospital stay
- Hospital readmission for any reason
- Device- and surgery-related adverse events
- Active straight leg raise (ASLR) assessment

### 8.3.3 Safety Endpoints

Device- and surgery-related adverse events (AE), as indicated by the Investigator.

### 8.3.4 Other Endpoints

The re-operation rate in older patients vs. younger patients for a given fracture type for both the displaced and non-displaced fracture types.

## 8.4 VISITS AND EXAMINATIONS

### 8.4.1 Summary

For a summary of the required procedures by visit, refer to Table 8.4.1-1: Study Procedures by Visit.

**Table 8.4.1-1: Study Procedures by Visit**

Schedule of events	Pre-Operative Data (Day -7 to Day 0)	Operative/Discharge Data  (Day 1)	6 weeks (Day 42 ± 7 days)	3 months (Day 90 ± 7 days)	6 months (Day 180 ± 14 days)	12 months (Day 365 ± 30 days)
Informed Consent	✓					
Inclusion/Exclusion	✓					
Demographics/ Medical History	✓					
Operative Data Collection		✓				
Discharge Data Collection 		✓				
VAS (pain score)	✓		✓	✓	✓	✓
Timed Up & Go			✓	✓	✓	✓
EQ-5D-5L	✓		✓	✓	✓	✓
X-Ray 
 
• AP
 
• Lateral
 
	✓	✓	✓	✓	✓	✓
Active Straight Leg Raise			✓	✓	✓	✓
Adverse Event Assessment		✓	✓	✓	✓	✓
End of Study/Exit						✓

 Discharge data to be collected at time of discharge which will be dependent on subject recovery.

#### 8.4.2 Screening/Preoperative Visit

NOTE: Any subject who signs an informed consent but fails to meet the required entry criteria is considered to be a Screen Failure. Screen Failure subjects will be assigned subject numbers and their demographic information will be captured in the appropriate CRF with the reason for screen failure specified.

1. Obtain written informed consent from the subject as detailed in Section 7.4  
**----- Do not proceed until consent has been obtained -----**
2. Obtain demographic information and medical history, including information on all concomitant medications/therapies and pre-injury ambulatory status.
3. Screen the subject for protocol inclusion/exclusion criteria.
4. If subject meets protocol inclusion/exclusion criteria, assign a subject number using format SS-NNN (SS = site number, NNN subject number at site). The subject number will be assigned in sequential order starting with 001. Screened subject numbers will NOT be reused by qualifying subjects.
5. Perform radiology imaging collecting both anteroposterior (AP) and lateral images of the target hip.
6. Assess level of pain from the target hip within the previous 24 hours using the Visual Analog Scale (VAS).
7. Instruct the subject to complete the health outcome questionnaire, EQ-5D-5L.
8. Instruct the subject on treatment procedures.
9. Subjects will return to the treatment facility, if applicable, for the Baseline /Operation Visit no longer than 7 days post-fracture.

#### 8.4.3 Baseline/Operation Visit (Day 1)

NOTE: If the Investigator decides a subject should not receive the Study Device for any reason at the time of surgery, the subject will be considered a Screen Failure and the reason for non-enrollment will be clearly documented in the subject's source documents.

1. Query subject regarding any changes in general health and the use of concomitant medications.
2. If any adverse device effects or device deficiencies are observed or reported, they must be recorded as instructed in Section 11, adverse events and device deficiencies.
3. Perform surgery per current CONQUEST FN™ Instructions for Use (IFU).
4. Collect study-specific operative data.
5. Perform radiology imaging collecting both anteroposterior (AP) and lateral images of the target hip to ensure the CONQUEST FN™ is properly implanted.
6. Collect study-specific discharge data.
7. Instruct the subject on proper postoperative care documenting the prescribed rehabilitation plan in the subject's source document.
8. Instruct the subject on follow-up procedures, including returning to the office for Follow-up (FU) Visit 1 in 42 ( $\pm$  7) days.

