### CONFIDENTIAL AND PROPRIETARY

This document contains information that is confidential and proprietary to Smith & Nephew PLC and Smith & Nephew, Inc. and is intended for use only by Smith & Nephew and its manufacturer. It shall not be reproduced or copied in whole or in part, nor shall the contents be disclosed by any means without prior written permission from Smith & Nephew, nor shall anyone make any use of it that is contrary to the expressed or implied wishes of Smith & Nephew.

Study Protocol—Device	
A Multicenter, Post Market, Prospective Study Evaluating Safety and Efficacy of CONQUEST FN™ for the Treatment of Intracapsular Femoral Neck Fractures	Number: 18-3047-02
	Version: 2.0, 30Nov2018
	Page: Page 19 of 63

- 5. Subject, in the opinion of the Investigator, has an emotional or neurological condition that precludes cooperation and compliance with the rehabilitation regimen.
- 6. Therapy with another investigational agent within thirty (30) days of Screening or planned therapy with another investigational agent during the course of the study.
- 7. Subject has a physical condition that, in the opinion of the Investigator, would preclude adequate implant support or impede healing (e.g. blood supply impairment, insufficient bone quality or quantity, or an active, local or systemic infection). If this is identified at the time of surgery, the subject will be screen failed.
- 8. Subject has undergone previous surgery on the target hip.
- 9. Subject has a severe bow of the target hip or gross distortion of the femur.
- 10. Subjects who have participated previously in this clinical trial and who have healed or been withdrawn.
- 11. Current systemic therapy with cytotoxic drugs.
- 12. Subjects with a history of poor compliance with medical treatment.
- 13. Subjects with a medical or physical condition that, in the opinion of the Investigator, would preclude safe subject participation in the study.

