#### **7.5 ENROLLMENT**

Enrollment in this study shall occur once the subject has successfully completed the informed consent process and successfully completed the Operative Visit (Day 1). A subject number will be assigned at the time of the Screening visit.

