## 9.2 ANALYSIS POPULATIONS

- Intention to Treat population (ITT), including all subjects randomized into the study.
- Full analysis set population (FAS), following Intention to Treat principle including all subjects who were randomized into the study and attended at least one post-baseline assessment
- Safety Population (SAF), including all subjects who have received the IP or the control devices.
- Per-Protocol Population (PP), including all subjects in the full analysis set who have no significant protocol deviations and met the inclusion/exclusion criteria.

Statistical analysis will be performed using each of the patient populations as follows. Analysis of the primary, secondary and exploratory efficacy objectives will be performed separately using both the Full Analysis Set and the Per Protocol Population. All safety analyses will utilize the Safety Population.

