#### 9.4.2 Analysis of Secondary Endpoint(s)

The rate or mean of the following outcomes at 1 year post-operation will be reported:

- Intraoperative complications
- Radiographic outcomes including quality of fracture reduction
- Construct failure past typical femoral neck fracture healing period (past 6 months)
- Visual analogue scale (VAS) relating to pain at the fracture site
- Quality of Life (EQ-5D-5L)
- Time to return to full weight-bearing
- Ambulatory status from pre-injury to study completion
- Timed Up & Go
- Length of hospital stay
- Hospital readmission for any reason
- Device and surgery related adverse events
- Active straight leg raise (ASLR) assessment

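### As written, the Screen Failure and enrolment rules can leave a started-then-abandoned CONQUEST FN implantation out of the intraoperative-complication rate; the SAP should define an attempted-implantation set

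*Combined protocol and SAP*

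**What the plan says.** Four parts of the protocol bear on this.

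- **Status at surgery.** Section 8.4.3 sets the rule for an Investigator's decision at operation: "decides a subject should not receive the Study Device for any reason at the time of surgery, the subject will be considered a Screen Failure". It describes the result as non-enrolment. Section 7.2, exclusion 7 (a physical condition that would compromise implant support or healing) adds: "If this is identified at the time of surgery, the subject will be screen failed". Section 7.5 places enrolment after the subject has "successfully completed the informed consent process and successfully completed the Operative Visit (Day 1").
- **Endpoint.** Intraoperative complications are a secondary endpoint (Section 8.3.2). They are listed in Section 9.4.2, within the efficacy analysis: "The rate or mean of the following outcomes at 1 year post-operation will be reported".
- **Analysis sets.** Section 9.2 states: "Analysis of the primary, secondary and exploratory efficacy objectives will be performed separately using both the Full Analysis Set and the Per Protocol Population". It defines the Full Analysis Set (FAS) as "including all subjects who were randomized into the study and attended at least one post-baseline assessment", and the Per-Protocol set (PP) is a subset of it. The Safety Population is described as "including all subjects who have received the IP or the control devices". Safety analyses use only the Safety Population (Sections 9.2 and 9.5).
- **Recording and reporting.** Adverse device effects and device deficiencies at the operative visit must be recorded (Section 8.4.3, step 2). All adverse events and deficiencies go into the CRF and adverse events are medically reviewed (Section 11.2). For a Screen Failure, Section 8.4.2 names only demographics and the reason as CRF content. Section 9.3 promises an accountability report covering losses to follow-up, deaths, revisions and withdrawals, with its methods left to the SAP. Section 9 leaves the detail of all analyses to a SAP to be finalised before database lock.

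**The concern.** The Screen Failure note does not separate a decision taken before the device is used from an implantation that was begun and then given up. An intraoperative complication or a device malfunction can be the very reason for giving up. Whether an operation enters the denominator could then depend on the outcome being measured. The rate at stake is the intraoperative-complication rate, and possibly the device-deficiency summary, in a study whose secondary objective is safety and performance evidence for this device. Operations that went badly enough to be abandoned would be the ones missing.

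**Working it through.** The plan states no figure that depends on this point, so the check has two parts: which sets a case enters, and how far the rate could move.

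**Set membership.** Section 8.2 says "This study is not randomized", so the FAS definition cannot be applied literally. That wording affects every subject and is a separate matter; here *randomized* is read as *enrolled*.

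| Case | Enrolled (7.5, 8.4.3) | FAS / PP (9.2) | Safety Population (9.2) |
|---|---|---|---|
| Decision made before the device is used | No | Out | Out, as one would expect |
| Attempt abandoned before any component is placed | No, as written | Out | Does not fit *received* on its face |
| Component placed, then removed in the same operation | No, as written | Out | Depends on *received*, which is undefined |
| Device implanted | Yes | FAS: in, given one post-baseline assessment; PP: also subject to its own conditions | In |

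The Safety Population is not tied to enrolment, and Section 11.1.1 defines an adverse event by use of the device. The third row could therefore be counted.

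The sets that apply to intraoperative complications are themselves open. Their place under Section 9.4 points to FAS and PP. But Section 8.3.2 describes the secondary endpoints as including safety evidence, and the same list contains the device- and surgery-related adverse events that Section 8.3.3 makes the safety endpoint. So there are two branches:

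- Analysed on FAS and PP: the second and third rows are both excluded.
- Analysed as safety: the third row turns on *received*, and the second row is probably excluded.

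**Size.** Let 90 be the implanted subjects (the minimum enrolment, Section 10), k the abandoned attempts, and p_I and p_A the complication proportions in implanted and abandoned cases. Section 7.7.1 replaces subjects who drop out before enrolment, so an abandoned attempt would arguably be replaced and the 90 preserved.

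All-attempt rate = (90 × p_I + k × p_A) / (90 + k)

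Understatement = all-attempt rate − p_I = k/(90 + k) × (p_A − p_I)

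The documents give neither k nor any complication rate. For an assumed k the weight k/(90 + k) is:

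- k = 0: 0
- k = 1: 1/91 = 1.10%
- k = 3: 3/93 = 3.23%
- k = 5: 5/95 = 5.26%

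Since p_A − p_I cannot exceed 1, these weights are also ceilings in percentage points. A ceiling is reached only if every abandoned case and no implanted case has a complication.

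Illustration with an assumed 3 complications in 90 implanted (3/90 = 3.33%) and c complications among the k abandoned:

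| k | c | All-attempt rate | Change (points) |
|---|---|---|---|
| 1 | 0 | 3/91 = 3.30% | −0.04 |
| 1 | 1 | 4/91 = 4.40% | +1.06 |
| 5 | 0 | 3/95 = 3.16% | −0.18 |
| 5 | 2 | 5/95 = 5.26% | +1.93 |
| 5 | 5 | 8/95 = 8.42% | +5.09 |

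The sign depends on p_A − p_I. With no complications among abandoned attempts, leaving them out raises the reported rate slightly. The approximately 60 earlier cases in Section 4.1 are implanted cases and say nothing about how often an attempt is abandoned.

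**The case against.** The strongest reply is that the protocol does not describe this case at all. Section 8.4.2 defines a Screen Failure as a consented subject who does not meet the entry criteria, and a technical or device problem during implantation is not an entry-criteria failure. The note in Section 8.4.3 stands ahead of the visit steps, including the surgery step, and the one worked example, exclusion 7, concerns patient suitability. On that view the note covers unsuitable patients only. This has weight as to intent. It does not settle the matter, because the note's wording is wider and Section 7.5 independently ties enrolment to a successfully completed operative visit.

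A second reply is that the events are not lost. Section 11.2 requires CRF entry of all adverse events and deficiencies, with adverse device effects, serious events and deficiencies reported to the Sponsor within 24 hours, and neither duty is limited to enrolled subjects. Step 4 of Section 8.4.3 already calls for operative data. That stands: the gap is in the analysis denominator and the reporting, with some doubt about the operative page because of the short CRF list for Screen Failures.

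A reader might go further and infer that the plan removes abandoned operations from every analysis, or that no table will show them. The documents do not support either. The Safety Population may admit a device placed and removed, and Sections 9 and 9.3 leave the methods to a SAP whose text is not part of what was reviewed. The most that can be said is that the current text makes no commitment to summarise these cases.

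**Conclusion.** The point holds in a limited form. Following the stated rules, a started-then-abandoned implantation is outside any set built on enrolment, and whether it enters the Safety Population rests on one undefined word. Calling the complication rate biased would go too far. Understatement requires that such cases occur and that they carry more events than completed implantations; the documents give no evidence on either. The ceilings of 1.1 to 5.3 points rest on an assumed k of 1 to 5 and the minimum enrolment of 90. The same condition applies to the device-deficiency summary, and there only if *received* does not cover these cases. The primary re-operation rate is unaffected, because it concerns fractures treated with the device. This is a minor point about the denominator of one descriptive secondary endpoint, and possibly one safety summary, and a cheap improvement.

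**What to change.** Mainly in the SAP, before database lock:

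- Define an attempted-implantation set: consented subjects in whom a CONQUEST FN component or device-specific instrument was introduced.
- On that set, report intraoperative complications, device deficiencies, and the number of and reasons for abandoned attempts.
- State whether a device placed and removed in the same operation counts as received for the Safety Population.
- List abandoned attempts in the accountability report of Section 9.3.
- Keep implanted subjects as the denominator for the re-operation rate.

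In addition, make clear through the CRF completion guidance, or at the next amendment, that the operative page is completed for these subjects. An amendment for this alone is not needed; Section 14 reserves amendments for exceptional cases once the study has started. The CRF guidance should come early, since operative data not collected at the time may be hard to recover.

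The cost is one set definition, one table and operative pages for what may be few or no extra subjects. The downside is a little more analysis and a complication rate that may look less favourable.

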#### 8.4.4 Follow-up Visits: 6 Weeks (Day 42 $\pm$ 7 days), 3 Months (Day 90 $\pm$ 7 days), 6 Months (Day 180 $\pm$ 14 days)

1. Assess level of pain from the target hip within the previous 24 hours using the VAS.
2. Instruct the subject to complete the health outcome questionnaire, EQ-5D-5L.
3. Complete active straight leg raise (ASLR) test as instructed in Section 8.5, Study Methods and Measurements.
4. Complete Timed Up and Go (TUG) test as instructed in Section 8.5, Study Methods and Measurements.

#### CONFIDENTIAL AND PROPRIETARY

This document contains information that is confidential and proprietary to Smith & Nephew PLC and Smith & Nephew, Inc. and is intended for use only by Smith & Nephew and its manufacturer. It shall not be reproduced or copied in whole or in part, nor shall the contents be disclosed by any means without prior written permission from Smith & Nephew, nor shall anyone make any use of it that is contrary to the expressed or implied wishes of Smith & Nephew.

Study Protocol—Device	
A Multicenter, Post Market, Prospective Study Evaluating Safety and Efficacy of CONQUEST FN™ for the Treatment of Intracapsular Femoral Neck Fractures	Number: 18-3047-02 Version: 2.0, 30Nov2018 Page: Page 28 of 63

5. Query subject regarding any changes in general health, the use of concomitant medications, and ambulatory status
6. If any adverse device effects or device deficiencies are observed or reported, they must be recorded as instructed in Section 11, adverse events and device deficiencies.
7. Perform radiology imaging collecting both anteroposterior (AP) and lateral images of the target hip.
8. Instruct the subject on proper postoperative care documenting continued instructions in the subject's source document.
9. Instruct the subject on follow-up procedures, including returning to the office for FU Visit 2 in 90 ( $\pm$  7) days and Visit 3 in 180 ( $\pm$  14) days

#### **8.4.5 Exit Visit: 12 months (Day 365 $\pm$ 30 days)**

1. Assess level of pain from the target hip within the previous 24 hours using the VAS.
2. Instruct the subject to complete the health outcome questionnaire, EQ-5D-5L.
3. Complete ASLR test as instructed in Section 8.5, Study Methods and Measurements.
4. Complete TUG test as instructed in Section 8.5, Study Methods and Measurements.
5. Query subject regarding any changes in general health, the use of concomitant medications, and ambulatory status
6. If any adverse device effects or device deficiencies are observed or reported, they must be recorded as instructed in Section 11, adverse events and device deficiencies.
7. Perform radiology imaging collecting both AP and lateral images of the target hip.
8. Complete Exit Visit CRF

#### **8.4.6 Unscheduled Visits**

Unscheduled examinations may be conducted at the discretion of the Investigator with all obtained information recorded in the source documents and on the appropriate CRF.

#### **8.4.7 Concomitant Medications and Therapies**

##### **CONFIDENTIAL AND PROPRIETARY**

This document contains information that is confidential and proprietary to Smith & Nephew PLC and Smith & Nephew, Inc. and is intended for use only by Smith & Nephew and its manufacturer. It shall not be reproduced or copied in whole or in part, nor shall the contents be disclosed by any means without prior written permission from Smith & Nephew, nor shall anyone make any use of it that is contrary to the expressed or implied wishes of Smith & Nephew.

Study Protocol—Device	
A Multicenter, Post Market, Prospective Study Evaluating Safety and Efficacy of CONQUEST FN™ for the Treatment of Intracapsular Femoral Neck Fractures	Number: 18-3047-02
	Version: 2.0, 30Nov2018
	Page: Page 29 of 63

A concomitant medication (e.g. drug, substance) and a concomitant therapy (e.g. physical therapy, TENS Unit, massage) are recorded pre-operatively and at each visit through the subject's last study visit. The subject's ambulatory status will be documented pre-operatively and at each follow-up through the last study visit.

#### **8.4.7.1        *Concomitant Medications***

##### **8.4.7.1.1      Excluded Concomitant Medications**

There are no excluded concomitant medications for this study.

##### **8.4.7.1.2      Recording Concomitant Medications in the CRF**

Only medications related to the IP implanted and medications used to treat an AE/ADE related to the IP will be recorded in the CRF. Reference the CRF Completion Guidelines for how medications are recorded.

#### **9.1.8 Discontinued Subjects**

Discontinued subjects are those who voluntarily discontinue participation, who are withdrawn for reasons of safety or use of prohibited concomitant treatments, or who are lost to follow-up.

Refer to section 7.8 for further details. Where possible, a full Exit Visit should be completed for all subjects who discontinue the study early. Where consent is withdrawn, the date and any reason given for discontinuation should be captured, at a minimum (see Section 7.7.1).

Any changes to medical health and/or the use of concomitant medications will be captured. If any SAE, SADE, or DevD were observed since the previous visit, they must be recorded (refer to section 11, Adverse Events and Device Deficiencies, for instructions on reporting and evaluation procedures). Finally, if appropriate, the Investigator will also advise the subject of subsequent therapy and/or procedures necessary for their medical condition.

